The starting dose of ruxolitinib was based on platelet count. Patients with a platelet count between 100 and 200 X 109/L were started on ruxolitinib 15 mg twice daily and patients with a platelet count greater than 200 X 109/L were started on ruxolitinib 20 mg twice daily. Doses were then individualized based upon tolerability and efficacy with maximum doses of 20 mg twice daily for patients with platelet counts between 100 to less than or equal to 125 X 109/L, of 10 mg twice daily for patients with platelet counts between 75 to less than or equal to 100 X 109/L, and of 5 mg twice daily for patients with platelet counts between 50 to less than or equal to 75 X 109/L.

Study 1

Study 1 was a double blind, randomized, placebo-controlled study in 309 patients who were refractory to or were not candidates for available therapy. The median age was 68 years (range 40 to 91 years) with 61% of patients older than 65 years and 54% were male. Fifty percent (50%) of patients had primary myelofibrosis, 31% had post-polycythemia vera myelofibrosis and 18% had post-essential thrombocythemia myelofibrosis. Twenty-one percent (21%) of patients had red blood cell transfusions within 8 weeks of enrollment in the study. The median hemoglobin count was 10.5 g/dL and the median platelet count was 251 X 109/L. Patients had a median palpable spleen length of 16 cm below the costal margin, with 81% having a spleen length 10 cm or greater below the costal margin. Patients had a median spleen volume as

Phase 2 - Ruxolitinib Page 11 of 67

measured by magnetic resonance imaging (MRI) or computed tomography (CT) of 2595 cm³ (range 478 cm³ to 8881 cm³). (The upper limit of normal is approximately 300 cm³).

Patients were dosed with ruxolitinib or matching placebo. The primary efficacy endpoint was the proportion of patients achieving greater than or equal to a 35% reduction from baseline in spleen volume at Week 24 as measured by MRI or CT.

Secondary endpoints included duration of a 35% or greater reduction in spleen volume and proportion of patients with a 50% or greater reduction in Total Symptom Score from baseline to Week 24 as measured by the modified Myelofibrosis Symptom Assessment Form (MFSAF) v2.0 diary.

Study 2

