4.4 Packaging and Labeling of Study Drugs

Drugs will be packaged and labeled per UCSF institutional standards, adhering to applicable local and federal laws.

5 Treatment Plan

5.1 **Dosage and Administration**

Treatment will be administered on an outpatient basis.

Table 5.1 Regimen Description

Study Drug	Dose	Route	Schedule	Cycle Length
Ruxolitinib	20mg or 15mg dependent on baseline	РО	BID	Pre-operative window (14-21 days) or up to 28 days for delayed
	platelet count			surgery

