5.2 Dose De-escalation Rule

A continuous monitoring rule for safety will be instituted, to guard against excess toxicity from pre-operative treatment with ruxolitinib at the FDA-indicated starting dose for patients with myelofibrosis (20 mg bid for patients with a platelet count \geq 200,000 or 15 mg bid for patients with a platelet count \geq 150,000 and < 200,000). See section 8.3.3 Safety Lead-In

Table 5.2 below describes the number of toxicity events per number of treated patients required to trigger the ruxolitinib de-escalation rule. Table 8 also shows the posterior probability that the rate exceeds 33%, and the binomial probability associated with the decision for an assumed

Phase 2 - Ruxolitinib Page 30 of 67

33% discontinuation rate. The prior probability has a beta distributions with parameters a = 1 and b = 9, assumes a 10% mean with an approximate 80% mid-range of .0 to .22.

Table 5.2 Boundaries for the De-Escalation Rule

Participants	Treatment-Related Discontinuations	PP(π > 33%)*	$Pr(X \ge r p = .33)$
6	5	.629	.017
8	6	.685	.019
11	7	.673	.037
14	8	.664	.054
17	9	.657	.071
20	10	.650	.087
23	11	.645	.101
27	12	.594	.145
30	13	.592	.156
33	14	.590	.167

 $^{^*\}pi$ is the discontinuation rate. The minimum acceptable upper bound of a treatment-related discontinuation is 33%. PP(π > 33%) is the posterior probability that the discontinuation rate exceeds this 33% upper bound. This posterior probability of discontinuation is calculated from the prior distribution, the number of participants treated and the observed number of treatment-related discontinuations.

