5.3 Procedures in Case of Overdose

There are no known antidotes for ruxolitinib. The treatment of AEs associated with overdose should be supportive for the underlying adverse symptoms.

Single doses up to 200 mg have been given with acceptable acute toxicity. Doses of study treatment in excess of that specified (20 mg twice daily) in the clinical study protocol are considered to be an overdose. Overdose, with or without associated symptoms, should be handled in the same way as a SAE. Signs or symptoms of an overdose that meet the criteria of SAE should be reported as a SAE in the appropriate manner and be documented as clinical sequelae to an overdose.

5.4 **Procedures in Case of Pregnancy**

Pregnancy in itself is not regarded as an AE unless there is a suspicion that an investigational product may have interfered with the effectiveness of a contraceptive treatment. All reports of congenital abnormalities/birth defects are SAEs. Any SAE experienced during pregnancy must be reported on the SAE Report Form. Elective terminations for medical reasons, and any serious complications of pregnancy (including spontaneous miscarriage) should be reported as SAEs. Elective abortions without complications should not be handled as SAEs.

The time period for collecting information on the occurrence of a pregnancy is from first administration of study treatment up to and including the follow up period. The outcome of all pregnancies (spontaneous miscarriage, elective termination, normal birth or congenital abnormality/birth defects) must be followed up and documented even if the participant was discontinued from the study.

Phase 2 - Ruxolitinib Page 31 of 67

5.5 **Dose Modifications and Dosing Delays**

The following dose modification rules will be used with respect to potential toxicity. Toxicity will be assessed according to the NCI Common Terminology Criteria for Adverse Events Version 4.0 (CTCAE v4.0).

Ruxolitinib is approved for use in myelofibrosis at the dose of 20 mg po bid when the baseline platelet count > 200,000, 15 mg po bid when the baseline platelet count is > 100,000 but \leq 200,000, and 5 mg bid when the baseline platelet count is > 50,000 but \leq 100,000. Ruxolitinib is approved in polycythemia vera at the dose of 10 mg po bid.

Dose reductions will not be allowed. Treatment delays up to 1 week are permitted as follows:

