- e. Within 6 weeks of study entry (within 4 weeks preferred), and again within 5 days prior to planned surgery, patients will undergo cross-sectional radiological evaluation using diagnostic contrasted CT, PET/CT (with diagnostic contrasted CT), or MRI of regions with radiologically or clinically identifiable tumor. The minimum cross-sectional evaluation is a diagnostic, contrasted computed tomography (CT) scan of the neck. PET/CT is the preferred modality, **provided it includes a diagnostic, contrasted CT scan of the neck** however is not mandatory. For patients with severe allergy to iodinated contrast dye despite premedication, or in the case of physician preference, neck MRI may be substituted. The pre- and post-treatment imaging modality should be the same, i.e. if MRI was used at study entry, it should be used at the post-treatment, pre-surgical assessment. **NOTE**: in the event that a patient lacks a CT-measurable primary tumor or metastatic lymph node, measurable disease may also be established by caliper measurement of an oral cavity or oropharyngeal tumor (≥ 1 centimeter). In this case, caliper measurement should be repeated within 5 days prior to planned surgery.
- f. The first day of ruxolitinib treatment will be considered Day 1. Ruxolitinib will be administered at 20 mg po bid, for 1421 days, and will be discontinued on the day of surgical resection (following the morning dose). If surgery is delayed, the study drug may be continued until surgery, for a maximum of 28 days. The interval between the last dose of ruxolitinib and surgery will be 2-24 hours.
- g. Surgery will be scheduled during days 14-21 of ruxolitinib treatment. For logistical reasons, surgery may be delayed by up to 7 days. Postoperative complications, hospital days, and ICU days will be noted for each patient.
- h. Research blood samples will be obtained at screening and within the 5 days prior to scheduled surgery. One (1) purple top EDTA tube will be collected at each time point. Please refer to the laboratory SOPs for processing instructions.
- i. Archival tissue if available. If no archival tissue is available participants must undergo tissue biopsy at baseline. Research biopsies obtained at screening during planned surgery for resection of the tumor will be divided into fresh, fresh-frozen and paraffin specimens.

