6.3.2 Treatment Period

Days 1-28; **NOTE** ruxolitinib treatment is planned for 14-21 days, however may be administered up to 28 days if required for logistical/scheduling purposes.

6.3.2.1 **Day 1**

Ruxolitinib will be administered at the FDA-approved dose in myelofibrosis, as determined by baseline platelet count: 1) Patients with a platelet count ≥ 200,000 will take 20 mg bid (four 5mg tablets in the morning and four 5mg tablets in the evening); 2) participants with a platelet count ≥ 150,000 and < 200,000 will take 15 mg bid (three 5 mg tablets in the morning and three 5 mg tablets in the evening). Ruxolitinib will be discontinued on the day of surgical resection (following the morning dose). If surgery is delayed, the study drug may be continued until surgery, for a

Phase 2 - Ruxolitinib Page 38 of 67

Protocol CC# 16201

maximum of 28 days. Fourteen days is the minimum required treatment for a patient to be considered evaluable. The interval between the last dose of ruxolitinib and surgery will be 2-24 hours.

Ruxolitinib will be dispensed as 5mg tablets. Participants with a platelet count \geq 200,000 will take 20 mg bid (four 5mg tablets in the morning and four 5mg tablets in the evening). Participants with a platelet count \geq 150,000 and < 200,000 will take 15 mg bid (three 5 mg tablets in the morning and three 5 mg tablets in the evening).

Participants will be asked to indicate on a drug diary (see Appendix 4) when doses of study drug are taken in order to monitor for compliance. Participants may also use the drug diary for notations on side effects and other treatment related events.

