8.2.3 Safety Lead-in

A continuous monitoring rule for safety will be instituted, to guard against excess toxicity from pre-operative treatment with ruxolitinib at the FDA-indicated starting dose for patients with myelofibrosis (20 mg bid for patients with a platelet count \geq 200,000 or 15 mg bid for patients with a platelet count \geq 150,000 and < 200,000). The first cohort of 6 patients will be treated at this starting dose. After enrollment of the 6th patient, we will continuously monitor the number of

Phase 2 - Ruxolitinib Page 49 of 67

patients who discontinue ruxolitinib and come off study for ruxolitinib-attributable toxicity. A qualifying toxicity must be at least possibly related to ruxolitinib, as judged by the treating investigator, and fulfill one of the following definitions:

- Grade ≥ 3 non-hematologic toxicity, with the exception of asymptomatic electrolyte abnormalities manageable with repletion.
- Intolerable non-hematologic toxicities of any grade, which persist despite optimal medical management.
- Grade ≥ 3 thrombocytopenia or neutropenia.

If the posterior probability of \geq 33% toxicity rate exceeds 50% for patients having to discontinue window treatment due to qualifying toxicity, this would be considered unacceptable and would result in de-escalating the starting dose of ruxolitinib to 10 mg p.o. bid, the FDA-indicated starting dose in polycythemia vera, for all subsequent patients. This would be the starting dose in all patients with a qualifying platelet count for this study (\geq 150,000), including those with platelet count \geq 150,000 and < 200,000 and those with platelet count > 200,000. (see section 5.2 Dose De-Escalation Rule)

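### The overdose limit in section 5.3 is above 20 mg twice daily for everyone, so a patient assigned 15 mg who takes 20 mg twice daily (33% over) is not counted as overdosed

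*Combined protocol and SAP*

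**What the plan says.** Section 5.3 states that doses "in excess of that specified (20 mg twice daily) in the clinical study protocol are considered to be an overdose". It adds: "Overdose, with or without associated symptoms, should be handled in the same way as a SAE".

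The assigned dose is not the same for all patients. Table 5.1 (section 5.1) gives "20mg or 15mg dependent on baseline" platelet count. Section 6.3.2.1 states that patients with platelets of at least 150,000 but under 200,000 "will take 15 mg bid (three 5 mg tablets in the morning and three 5 mg tablets in the evening"; those at 200,000 or more take four 5 mg tablets per dose. Sections 1.3, 5.2 and 8.2.3 repeat this split. Section 8.2.3 adds a possible third dose: an unacceptable toxicity signal "would result in de-escalating the starting dose of ruxolitinib to 10 mg p.o. bid" for all later patients.

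Footnote f of the study calendar (section 6.1) gives one dose with no platelet condition: "Ruxolitinib will be administered at 20 mg po bid".

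**The concern.** Section 5.3 defines overdose as departure from the protocol dose, then gives that dose as a single figure that is right for only one of the two starting groups. For the 15 mg group the limit sits one tablet per dose too high.

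What is at stake is the reporting of the excess dose itself. Under section 7.3.2.3 an SAE goes on a MedWatch form to the monitoring committee, IRB, FDA and drug supplier. The supplier is told within 24 hours (section 7.7) and the coordinating center within 1 business day (Appendix 2, section 3.2). A symptomless excess in a 20 mg patient gets this handling; the same one-tablet excess in a 15 mg patient does not. Two sites, one following the literal figure and one following the likely intent, would report the same event differently.

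The error is easy to picture. All patients receive the same 5 mg tablets, and anyone dosing from calendar footnote f alone would give 20 mg to a 15 mg patient.

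**Working it through.** Section 5.3 offers no derivation of its limit to reproduce, so the check sets the limit against each assigned dose.

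**Inputs.** Overdose limit: above 20 mg twice daily (5.3). Assigned doses: 20 mg or 15 mg twice daily (5.1, 6.3.2.1), or 10 mg twice daily after de-escalation (8.2.3). Tablet strength: 5 mg. Treatment: 14 to 21 days, at most 28. Enrollment: 45 (3.2).

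**Largest excess not classed as an overdose** = limit / assigned dose − 1.

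| Assigned (twice daily) | Limit in 5.3 | Excess not caught |
|---|---|---|
| 20 mg (8 tablets/day) | 20 mg | 20/20 − 1 = 0% |
| 15 mg (6 tablets/day) | 20 mg | 20/15 − 1 = 33% |
| 10 mg (4 tablets/day) | 20 mg | 20/10 − 1 = 100% |

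**Ceiling on total excess for a 15 mg patient.** 8 − 6 = 2 tablets a day. Over 14, 21 or 28 days that is 28, 42 or 56 tablets, or 140, 210 or 280 mg. This assumes the extra tablet is taken at every dose throughout.

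**Patients under the mismatched limit.** The documents do not give the share with platelets of 150,000 to under 200,000. Assuming 10% to 30%: 0.10 × 45 = 4.5 and 0.30 × 45 = 13.5, so about 5 to 14. These are patients assigned 15 mg, not patients expected to exceed their dose.

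**Is the 10 mg row likely to arise?** Section 5.2 states: "The prior probability has a beta distributions with parameters a = 1 and b = 9". After r treatment-related discontinuations in n patients the posterior is Beta(1 + r, 9 + n − r), and the rule triggers when P(rate > 33%) exceeds 50%. For the first row of Table 5.2 (n = 6, r = 5), Beta(6, 10) gives P(rate > 0.33) = 0.629, and the binomial P(X ≥ 5 of 6) at 0.33 is 0.017. Both match the table, as do the other nine rows. The exact chance of ever crossing was then computed in two ways: looking only at the ten tabulated sample sizes (to 33 patients), and looking after every patient from 6 to 45.

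| True discontinuation rate | Table 5.2 rows only | After every patient |
|---|---|---|
| 10% (prior mean) | 0.00010 | 0.00038 |
| 20% | 0.0100 | 0.0252 |
| 33% | 0.235 | 0.403 |
| Averaged over Beta(1,9) | 0.0207 | 0.0329 |

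The 33% gap for 15 mg patients therefore exists from day 1. The 100% gap is contingent, and improbable unless toxicity is far worse than the protocol expects.

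**The case against.** Four arguments can be made for the current text.

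First, the dose specified in the protocol could be read as each patient's own dose, with the bracketed figure naming only the usual one. That may be what was meant. But the bracket fixes the figure at 20 mg twice daily and no other section overrides it. If the assigned dose was intended, the bracket is wrong and needs the same edit.

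Second, a single ceiling at the highest protocol dose could be deliberate. Section 1.2 reports that the Phase 3 myelofibrosis studies allowed "maximum doses of 20 mg twice daily for patients with platelet counts between 100 to less than or equal to 125" × 10⁹/L, below the platelet counts enrolled here, and 5.3 notes that single doses up to 200 mg had acceptable acute toxicity. This stands as a reason to claim no particular harm. It does not explain the rule: 5.3 treats any excess over the protocol dose as an overdose despite that tolerability, so its test is departure from the plan, not a toxic threshold.

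Third, excess dosing would still be seen. Pill counts and diaries are checked before surgery, protocol violations are discussed on monthly multicenter calls (Appendix 2), and adverse events from any dose are recorded. This stands, and limits the loss to the automatic SAE-type handling. The calendar schedules no clinic visit or blood test between screening and the pre-surgery visit, so the pill count and diary check would usually come late.

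Fourth, footnote f is a separate fault, and it shows only how an error could occur, not how often. That also stands.

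**Conclusion.** The concern holds. As written, 5.3 is wrong for patients assigned less than 20 mg twice daily and correct for those assigned 20 mg. For the 15 mg group it leaves up to a 33% excess outside the overdose definition. About 5 to 14 of 45 patients fall under the mismatched limit, on an assumed 10% to 30% share that the documents do not supply. The 100% gap at 10 mg depends on a de-escalation with a probability of 0.01% to 0.04% at the prior-mean rate.

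The importance is low. What is lost is a reporting trigger, not detection of toxicity. The primary analysis, alpha, power and analysis populations do not depend on it.

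**What to change.** In section 5.3, replace the fixed figure with the assigned dose, for example: *Any dose of study treatment above the patient's assigned dose (20 mg or 15 mg twice daily by baseline platelet count, or 10 mg twice daily after de-escalation) is considered an overdose.* These are the protocol's own doses; no new one is introduced. Adding the platelet condition to calendar footnote f at the same amendment would remove a likely source of the error.

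Nothing changes for 20 mg patients. The cost is some additional overdose reports, on SAE timelines, for 15 mg patients who exceed their dose, some of them symptomless and within the dose range used in Phase 3. That is the handling 20 mg patients already receive. If the sponsor thinks SAE-type handling of a single extra tablet is excessive, that is a question about the rule for all patients, not a reason to exempt one group.

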Duration of study	The study will reach completion 24 months from the time the study opens to accrual.		
Study Drugs	Ruxolitinib, JAKAFI®, INCB018424 (JAK 1/2 inhibitor) 20mg (or 15mg) PO BID.		
Safety Assessments	The safety of this window intervention will be reported descriptively, including tabulation of toxicities according to NCI CTCAE v.4, surgical complications, and length of hospital stay.		
Efficacy Assessments	Efficacy of neoadjuvant ruxolitinib in patients with operable HNSCC as determined by quantitative ΔT umor size reflective of a 35% reduction.		

Phase 2 - Ruxolitinib Page 4 of 67

List of Abbreviations

AE adverse event

AUC area under the curve BUN blood urea nitrogen

CBC complete blood cell (count)

CR complete response

CRC Clinical Research Coordinator

CRF case report form CSF cerebral spinal fluid

CT computerized tomography

CTCEA Common Terminology Criteria for Adverse Events

CTEP Cancer Therapy Evaluation Program
CTMS Clinical Trial Management System

DFS disease-free survival

DSMC Data and Safety Monitoring Committee

DSMP Data and Safety Monitoring Plan

ECOG Eastern Cooperative Oncology Group

FDA Food and Drug Administration

GCP Good Clinical Practice

HDFCCC Helen Diller Family Comprehensive Cancer Center

HGB hemoglobin

ICH International Conference on Harmonization

IND investigational new drug application

IRB Institutional Review Board

IV intravenous

MedDRA Medical Dictionary for Regulatory Activities

MRI magnetic resonance imaging
MTD maximum tolerated dose
ORR overall response rate
PD disease progression
PK pharmacokinetics

PO Per os (by mouth, orally)

PR partial response

PRC Protocol Review Committee (UCSF)

QOL Quality of Life

RBC red blood cell (count)

SD stable disease

[figure not shown]
WBC white blood cell (count)

Phase 2 - Ruxolitinib Page 5 of 67

Table of Contents

Pro	tocol	Signature Page	2
		Signature Page – Participating Sites	
Abs	stract	4	
List	of A	obreviations	5
		Contents	
1		roduction	
ı			
	1.1	Background on Indication	
	1.2	Background on RuxolitinibRationale for the Proposed Study	
	1.3	Correlative Biomarker Analysis	
	1.7	1.4.1 Primary Analysis	

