In this study, ruxolitinib will be administered for a short period of 2-3 weeks prior to planned surgical resection of HNSCC. The dose will be the FDA-approved dose in myelofibrosis, as determined by baseline platelet count: 1) Patients with a platelet count \geq 200,000 will take 20 mg bid (four 5mg tablets in the morning and four 5mg tablets in the evening); 2) participants with a platelet count \geq 150,000 and < 200,000 will take 15 mg bid (three 5 mg tablets in the morning and three 5 mg tablets in the evening). The brief treatment duration is within the expected window of time that elapses from initial patient evaluation by a surgeon to performance of surgery. In the phase 0 or window trial model, a paired specimen analysis permits ex vivo evaluation of target modulation and pharmacodynamic changes in downstream or parallel molecular pathways. This study design is optimal in order to assess the biochemical and immunomodulatory effects of ruxolitinib on HNSCC. Furthermore, predictive biomarkers can be developed as related to a clinical endpoint (Δ Tumor size) or a biochemical, pharmacodynamic endpoint (Δ Ki-67).

Ki-67 is a nuclear non-histone protein first characterized in 1991, which is expressed in proliferating human tissue. 14 Down-modulation of Ki-67 is a validated surrogate biomarker in neoadjuvant studies of targeted therapy in breast cancer. 15,16 Changes in Ki-67 observed in a neoadjuvant endocrine therapy study predicted the ultimate long-term disease-free survival advantage in the larger, adjuvant trial, whereas clinical response did not. 16,17 In HNSCC window trials, Ki-67 modulation has not been evaluated directly against clinical outcome. 18-20 An alternate surrogate biomarker to Ki-67, the TUNEL apoptotic index, was evaluated as the primary endpoint in a randomized window trial of lapatinib vs. placebo, prior to standard chemoradiotherapy in HNSCC. 18 Although apoptosis was increased by lapatinib, the increase was not significant against that seen in the placebo group. Notably, the Ki-67 proliferation index was significantly decreased by lapatinib vs. placebo. This is in line with results from our first window study in HNSCC evaluating erlotinib, erlotinib-sulindac or placebo – where Ki-67 reduction was significantly greater in the erlotinib arms vs. placebo. Collectively, these data suggest that proliferation is a worthwhile secondary endpoint for evaluation of biomarker correlations.

The Jak/STAT pathway in Head and Neck Cancer

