3.3.1 Inclusion Criteria

- Histologically or cytologically confirmed, primary or recurrent, head and neck squamous cell carcinoma, including variants. Patients must have at least one measureable lesion in accordance with RECIST 1.1 (tumor diameter ≥ 1 cm; short-axis lymph node diameter ≥ 1.5 cm) OR by caliper measurement (tumor diameter ≥ 1 cm). Any diagnostic pretreatment biopsy sample is acceptable including FNA.
- 2. Primary tumors of any head and neck (oral cavity, oropharynx, hypopharynx, or larynx) site will be included.
- 3. Surgical resection of head and neck must be planned, either as primary treatment or salvage. Patients must have submitted adequate pre-treatment archival or fresh tissue.
- 4. Age ≥ 18 years.
- 5. ECOG performance status 0-2 (See Appendix 1).

Phase 2 - Ruxolitinib Page 25 of 67

- 6. Women of childbearing potential (WOCBP) must have a negative serum pregnancy test (sensitivity ≤ 25IU HCG/L) within 4 weeks prior to registration and will be repeated within 72 hours prior to the start of study drug administration.
- 7. Persons of reproductive potential must agree to use and utilize an adequate method of contraception throughout treatment and for at least 12 weeks after study drug is stopped. Prior to study enrollment, women of childbearing potential must be advised of the importance of avoiding pregnancy during trial participation and the potential risk factors for an unintentional pregnancy.
- 8. Adequate hematologic, renal and hepatic function, as defined by:
 - a) Absolute neutrophil count (ANC) ≥ 1,500/ul, platelets ≥ 150,000/ul.
 - b) Creatinine $\leq 1.5 \text{ x}$ institutional upper limit of normal (ULN).
 - c) Bilirubin $\leq 1.5 \times \text{ULN}$, AST or ALT $\leq 2.5 \times \text{ULN}$.
- 9. Have signed written informed consent

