4.1 Description, Supply and Storage of Investigational Drugs

4.1.1 Ruxolitinib (JAKAFI®, INCB018424)

Ruxolitinib is dosed orally, every morning and every evening, and can be administered with or without food. If a dose is missed, the patient should not take an additional dose, but should take the next scheduled prescribed dose. In the case of emesis, the patient should not take an additional dose, but should take the next scheduled prescribed dose. For patients unable to ingest tablets, ruxolitinib can be administered through a nasogastric or percutaneous gastrostomy tube (8 French or greater) as follows:

- Suspend three or four 5 mg tablets (dose dependent according to platelet count, as described under "Study drug treatment" in section 5.2) in approximately 40 mL of water with stirring for approximately 10 minutes.
- Within 6 hours after the tablets have dispersed, the suspension can be administered through the feeding tube using an appropriate syringe.

The tube should be rinsed with approximately 75 mL of water. The effect of tube feeding preparations on ruxolitinib exposure during administration through a nasogastric tube has not been evaluated.

Participants will be asked to indicate on a drug diary (see Appendix 4) when doses of study drug are taken in order to monitor for compliance. Participants may also use the drug diary for notations on side effects and other treatment related events. The Investigational Pharmacy will maintain a drug accountability log to record ruxolitinib received, dispensed and/or destroyed. Unused drugs will be destroyed locally and will not be returned.

NOTE: for current information, please see the most recent version of the Investigator Brochure

Classification

Phase 2 - Ruxolitinib Page 28 of 67

Ruxolitinib is a Class I molecule under the Biopharmaceutical Classification System, with high permeability, high solubility and rapid dissolution characteristics. In clinical studies, ruxolitinib is rapidly absorbed after oral administration with maximal plasma concentration (C_{max}) achieved approximately 1 hour post-dose

Mechanism of Action

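### Study calendar footnote f gives 20 mg bid to everyone, but patients with platelets of 150,000 to <200,000 are meant to receive 15 mg bid (40 instead of 30 mg/day)

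*Combined protocol and SAP*

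**What the plan says.** The study calendar (Section 6.1, Table 6.1) has a ruxolitinib row marked with footnote f. That footnote states the dose as "Ruxolitinib will be administered at 20 mg po bid" and goes on to duration, the last dose on the day of surgery, and delayed surgery. It mentions neither a platelet count nor a second dose level.

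Elsewhere the dose depends on the platelet count:

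- Section 1.3: "The dose will be the FDA-approved dose in myelofibrosis, as determined by baseline platelet count", followed by the two strata.
- Section 6.3.2.1 (Day 1): "participants with a platelet count ≥ 150,000 and < 200,000 will take 15 mg bid". Patients at 200,000 or above take 20 mg bid, and tablet counts are given for each stratum.
- Sections 5.2 and 8.2.3: the same rule, including "15 mg bid for patients with a platelet count" of at least 150,000 and below 200,000.
- Abstract: "20mg (or 15mg) PO BID", without cut-offs.
- Table 5.1: "20mg or 15mg dependent on baseline" platelet count, without cut-offs.
- Section 4.1.1 (tube administration): three or four tablets, "dose dependent according to platelet count", without cut-offs.

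The eligibility floor in Section 3.3.1 is "platelets ≥ 150,000/ul".

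**The concern.** The calendar is a working table. The opening of Section 6 sends staff to it for the study procedures, and the study runs at more than one centre. A coordinator or pharmacist who takes the dose from the calendar alone would give an eligible lower-platelet patient a third more drug than planned in the weeks before surgery.

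The plan may not catch this. Section 5.3 counts as overdose only what exceeds 20 mg twice daily, so 20 mg bid given to a 15 mg patient would not clearly qualify. The calendar schedules one on-treatment blood test, within 5 days before surgery, which is late in the window.

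The lower stratum is also the one to watch. Section 5.6 reports grade 3 or 4 thrombocytopenia in 16.5% of myelofibrosis patients with baseline platelets of 100 to 200 x 10⁹/L, against 7.2% of those above 200. That compares baseline counts in another disease, not 15 mg with 20 mg. It shows why this group needs the right instruction, and says nothing about how much harm the footnote would do.

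**Working it through.** The point needs the dose statements set side by side and simple dose arithmetic. There is no power or error-rate figure to reproduce.

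**Inputs**

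- Tablet strength: 5 mg (Section 4.1.1, storage and handling; Section 6.3.2.1).
- Platelets ≥ 200,000: 4 tablets morning and evening (Section 6.3.2.1).
- Platelets ≥ 150,000 and < 200,000: 3 tablets morning and evening (Section 6.3.2.1).
- Footnote f: 20 mg twice daily, all patients (Section 6.1).
- Eligibility floor: 150,000/ul (Section 3.3.1).

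**Daily dose** = tablets per dose × 5 mg × 2

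| Platelets | Rule (6.3.2.1) | Footnote f | Difference |
|---|---|---|---|
| ≥ 200,000 | 4 × 5 × 2 = 40 mg | 20 × 2 = 40 mg | none |
| 150,000 to < 200,000 | 3 × 5 × 2 = 30 mg | 20 × 2 = 40 mg | +10 mg/day |

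In the lower stratum the ratio is 40/30 = 1.33, so the literal dose is 33% above the intended one: 8 tablets a day instead of 6.

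**Which statement is the outlier?** Four sections give the two-level rule with identical cut-offs (1.3, 5.2, 6.3.2.1, 8.2.3). Three further places provide for two doses without cut-offs (abstract, 4.1.1, Table 5.1). Footnote f is the only administration instruction with a single unconditional dose. Section 5.3 also mentions 20 mg twice daily without a platelet condition, but as the threshold for overdose. The intended rule is therefore not in doubt, and the footnote departs from it.

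**Can the affected patients enrol?** Yes. The floor of 150,000 is the lower edge of the 15 mg stratum, so the whole stratum is eligible.

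**Length of exposure.** Treatment is planned for 14-21 days, with a maximum of 28. Section 5.5 puts the onset of grade 3 or 4 thrombocytopenia at about 8 weeks (median), or 56 days. So 14/56 = 25%, 21/56 = 37.5% and 28/56 = 50%. According to Section 5.6, that median is among myelofibrosis patients who developed the event. These ratios place the treatment window against the usual time of onset; they are not risks.

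**The case against.** The best reply is that the instruction staff actually dose from is correct. Section 6.3.2.1 gives the Day 1 dose by stratum, states it twice and spells out the tablets. Table 5.1, the regimen table, says that the dose depends on platelets. The calendar is a summary, and most of footnote f concerns timing. A wrong dose would require someone to use the footnote and ignore both of the others. This stands as an argument about likelihood, and it is why the point is minor. It does not make the footnote correct.

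The clinical stakes are also modest. The window is short, grade 3 or worse thrombocytopenia stops the drug (Section 5.5), and the Phase 3 myelofibrosis studies allowed up to 20 mg twice daily at platelets of 100 to 125 x 10⁹/L, below this trial's floor (Section 1.2). That precedent is partial: 20 mg was a maximum reached by individual titration, and patients at 100 to 200 started on 15 mg. The blood test within 5 days before surgery would find a problem late and would not prevent the excess dose.

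Finally, it can be said that de-escalation and the overdose definition are separate topics. The overdose edit is separate, and is offered below as optional. The reference to de-escalation belongs in the fix, because under Section 8.2.3 all later patients would start at 10 mg bid, and a footnote naming only 20 and 15 mg would then be wrong for all of them.

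**Conclusion.** The inconsistency is confirmed and is minor. Footnote f is right for platelets of 200,000 or more and wrong for 150,000 to below 200,000, where it implies 40 instead of 30 mg/day (+33%). That figure is a dose difference and not an estimate of added risk.

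The conclusion assumes only that the rule stated in Sections 1.3, 5.2, 6.3.2.1 and 8.2.3 is the intended one, which their agreement supports. The documents do not give the share of patients expected in the lower stratum, so the number who could be affected is unknown. An actual misdose is unlikely given Section 6.3.2.1 and Table 5.1. The trial's design, error rate, sample size and analysis are not affected.

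**What to change.** Reword the dose in footnote f of Table 6.1 along these lines: *20 mg po bid if platelets are ≥ 200,000, or 15 mg po bid if platelets are ≥ 150,000 and < 200,000, as in Section 6.3.2.1, or the starting dose in force under Sections 5.2 and 8.2.3.* Section 6.3.2.1 does not mention the 10 mg bid de-escalated dose either, so the same closing reference could be added there to keep the two in step.

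Optional: in Section 5.3, define overdose as any dose above the patient's assigned dose, so that 20 mg bid in the 15 mg stratum would be captured and reported.

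The cost is one footnote and a notice to the sites, with no change to design, sample size or analysis.
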